#### **Missing Data:**

In the event a subject withdraws from the trial before Week 14 with no observed instances of a PDPE the number of PDPEs will be imputed using half the subject's historical (previous 12 months) PE count (rounded upwards) and their follow-up duration will be imputed as 26 weeks.

In the event a subject withdraws from the trial after Week 14 with no observed instances of a PDPE the number of PDPEs will be imputed using one quarter the subject's historical (previous 12 months) PE count (rounded upwards) and their follow-up duration will be imputed as 26 weeks.

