Event	Screening Visit 0	☎	Visit 1	☎	☎	Visit 2	☎	☎	Visit 3	☎	☎	☎	Visit 4	☎	IMP discontinuation visit ^a
Week	-5 to- 2	-1	0 ^b	2	4	6	8	12	14	16	20	24	26	27	
Visit window		± 1 day		± 3 days	± 3 days	± 7 days	± 3 days	± 3 days	± 7 days	± 3 days	± 3 days	± 3 days	- 7 days to + 28 days	± 1 day	Within 2 weeks of IMP discontinuation
Informed consent	X														
Inclusion/exclusion criteria	X														
Medical history / demographics	X														
Concomitant medications	X	X	X	X	X	X	X	X	X	X	X	X	X	X	X
Physical examination/ vital signs	X		X			X			X				X		X
Pulmonary function tests	X		X			X			X				X		X
Urine pregnancy test	X														
Pulmonary exacerbations review			X			X			X				X		X
MTT procedure	X														
Randomize subject			X ^c												
Dispense trial medication & bronchodilator			X			X			X						
Administer treatment dose in clinic			X			X			X				X		
Sputum qualitative microbiology	X														
Screening blood sample	X														

^a The IMP discontinuation visit is used for all subjects that discontinue IMP early, but are remaining in the study.

^b Subjects should be stable and clear of pulmonary exacerbations for at least two weeks prior visit 1. If a subject has an exacerbation after Visit 0 (screening), visit 1 should occur 2 to 5 weeks from the end of the treatment of the exacerbation or the end of the adverse event, whichever is later.

^c Randomize eligible subjects if compliance with maintenance therapies (antibiotic & rhDNase) is at least 80% in the two weeks prior to visit 1.

Event	Screening Visit 0	☎	Visit 1	☎	☎	Visit 2	☎	☎	Visit 3	☎	☎	☎	Visit 4	☎	IMP discontinuation visit ^a
Week	-5 to- 2	-1	0 ^b	2	4	6	8	12	14	16	20	24	26	27	
Visit window		± 1 day		± 3 days	± 3 days	± 7 days	± 3 days	± 3 days	± 7 days	± 3 days	± 3 days	± 3 day	- 7 days to + 28 days	± 1 day	Within 2 weeks of IMP discontinuation
Issue subject diary	X														
Review subject diary			X			X			X				X		X
Collect subject diary													X		
Adverse event assessment		X	X	X	X	X	X	X	X	X	X	X	X	X	X
Ease of expectoration VAS			X			X			X				X		X
CFQ-R respiratory domain			X			X			X				X		X
IMP compliance and accountability ^d						X			X				X		
Discuss adherence to treatment (if subject has discontinued IMP, schedule IMP discontinuation visit within 2 weeks of last IMP)				X	X		X	X		X	X	X			
Remind subject of next visit or phone call, withholding periods, to complete subject diary, and to return trial drug (if applicable) ^e		X	X	X	X	X	X	X	X	X	X	X	X		X

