10.2.9 Secondary analyses – missing data

Change from baseline FVC:

Missing post-baseline measurements will be handled as per the primary efficacy endpoint (FEV₁).

Time to first pulmonary exacerbation:

Subjects who withdraw from the trial prior to experiencing an exacerbation will be censored at the date of the last participation in the trial.

Pulmonary exacerbation rate:

In the event a subject discontinues from the trial before week 14 with no observed instances of a pulmonary exacerbations the number of pulmonary exacerbations will be imputed using half the subject’s historical (previous 12 months) pulmonary exacerbation count (rounded upwards) and their treatment exposure time will be imputed as 26 weeks.

In the event a subject discontinues from the trial after week 14 with no observed instances of a pulmonary exacerbations the number of pulmonary exacerbations will be imputed using one quarter the subject's historical (previous 12 months) pulmonary exacerbation count (rounded upwards) and their treatment exposure time will be imputed as 26 weeks.

Number of days in hospital and number of days on antibiotics:

Primary negative binominal analysis allows for different lengths of follow-up via offset variable. No further allowance for missing data will be made in these analyses.

Pulmonary exacerbation incidence:

No allowance for missing data will be made in this analysis.

Ease of expectoration:

Missing post-baseline measurements will be handled as per the primary efficacy endpoint (FEV₁).

CFQ-R respiratory domain score:

Missing post-baseline measurements will be handled as per the primary efficacy endpoint (FEV₁).

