## Statistical Analysis Plan

For rate of PDPE, if a subject withdraws from the trial before Week 14 with no observed instances of a PDPE the number of PDPEs will be imputed using half the subject's historical (previous 12 months) PE count (rounded upwards) and their follow-up duration will be imputed as 26 weeks. If a subject withdraws from the trial after Week 14 with no observed instances of a PDPE the number of PDPEs will be imputed using one quarter the subject's historical (previous 12 months) PE count (rounded upwards) and their follow-up duration will be imputed as 26 weeks.

For the secondary efficacy analyses of number of days on antibiotics due to PDPE, number of days in hospital due to PDPE, and incidence of PDPEs, no imputation of missing data will be performed.

Imputed data will not be displayed in data listings unless otherwise specified.

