#### Sensitivity Analysis 3: Multiple Imputation

To assess the possible impact of employing a single imputation method (i.e. risk of variability underestimation), an analysis based on MI will be performed.

For all subjects who withdrew from the trial with a follow-up duration shorter than 183 days (i.e. 26 weeks+1 day), the number of PDPEs from withdrawal up to day 183 will

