## Statistical Analysis Plan

Analysis Designation	Endpoint	Model	Imputation Process Used	Off-trial Medication Data Included	Analysis Set
Secondary 4 Hierarchical	Number of Days in Hospital Due to PDPE	Negative Binomial Model	None	Yes	ITT
Secondary 4 - Supportive	Number of Days in Hospital Due to PE	Negative Binomial Model	None	Yes	ITT
Secondary 4 - by Subgroups	Number of Days in Hospital Due to PDPE	Negative Binomial Model by Subgroups (see Section 6.6)	None	Yes	ITT
Secondary 5 Hierarchical	PDPE Rate	Negative Binomial Model	Half historical count over 26 weeks for withdrawals before Week 14 or one quarter historical count over 26 weeks for withdrawals after Week 14	Yes	ITT
Secondary 5 - Sensitivity 1	PDPE Rate	Negative Binomial Model	None	Yes	ITT

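### The main imputation rule for the PDPE rate has no upper time limit, so a PDPE-free subject who withdraws after the full 26 weeks, without Visit 4, can be scored with events

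*SAP*

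**What the plan says.** The fifth and last hierarchical secondary endpoint is the PDPE rate per person-year over the 26-week treatment period (SAP 4.2.1). It is analyzed with a negative binomial model whose offset is the log of follow-up duration (SAP 8.2.5).

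The late-withdrawal rule appears in four places, each with Week 14 as its only time condition:

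- SAP 8.2.5, Missing Data: a subject who "withdraws from the trial after Week 14 with no observed instances of a PDPE the number of PDPEs will be imputed using one quarter" of the "historical (previous 12 months) PE count (rounded upwards) and their follow-up duration will be imputed as 26 weeks".
- SAP 6.3: "If a subject withdraws from the trial after Week 14 with no observed instances of a PDPE the number of PDPEs will be imputed" in the same way.
- SAP Table 6, rows for the PDPE rate, its zero-inflated version and its subgroups, and for the supportive PE rate: "one quarter historical count over 26 weeks for withdrawals after Week 14".
- Protocol 10.2.9: a subject who "discontinues from the trial after week 14 with no observed instances of a pulmonary exacerbations" is handled by the same rule.

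Sensitivity Analysis 3 (SAP 8.2.5.1) does have a limit. It imputes only for withdrawals "with a follow-up duration shorter than 183 days (i.e. 26 weeks+1 day", and only for the time from withdrawal to Day 183.

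Three definitions determine who can fall under the main rule. The Visit 4 window is minus "7 days to + 28 days" around Week 26 (Protocol, Time and Events Schedule). A subject completes the trial by completing assessments up to Visit 4 (Protocol 9.1). The date of last participation is the completion or withdrawal date on the CRF, with no cap at 26 weeks (SAP 6.2.5).

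**The concern.** Imputation is meant to fill in the part of the 26-week period that was not observed. A subject followed without a PDPE to Day 183 has no such part. If that subject is then recorded as withdrawn before Visit 4, the literal rule replaces an observed zero with a positive count whenever there is any exacerbation history. It also discards event-free time already observed.

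The value assigned then depends on a label and not on the exacerbation record. Take two PDPE-free subjects, each with a prior-year count of 2 and each followed to Day 205. The one who completes Visit 4 contributes 0 events over 205 days. The one recorded as withdrawn contributes 1 event over 182 days.

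At stake are the main analysis of the endpoint, its subgroup and zero-inflated versions, and the supportive PE-rate analysis, which follows the same approach.

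**Working it through.** **Inputs.** Rule and rounding: SAP 8.2.5. Day 183 as 26 weeks plus one day: SAP 8.2.5.1, Sensitivity Analysis 3. Upper end of the Visit 4 window: SAP Table 4. Follow-up duration, last participation date minus Trial Day 1 plus 1: SAP 6.2.6. Let h be the prior-year exacerbation count.

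**Reproducing the plan's day counts.** 26 × 7 + 1 = 183, as stated in Sensitivity Analysis 3. 183 + 28 = 211, the upper limit for Visit 4 in SAP Table 4. So a subject can be past Day 183, not yet have had Visit 4, and still be within the window.

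**Events assigned.** The imputed count is ceil(h/4). Imputed follow-up is 26 × 7 = 182 days, and 182/365.25 = 0.498 years.

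| h | PDPEs observed | PDPEs assigned | Scored rate per person-year |
|---|---|---|---|
| 0 | 0 | 0 | 0 |
| 1 to 4 | 0 | 1 | 1/0.498 = 2.01 |
| 5 to 8 | 0 | 2 | 2/0.498 = 4.01 |

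**Follow-up removed.** The cut is (day of withdrawal − 182) days.

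| Withdrawal day | Unobserved days before Day 183 | Days cut | Share of observed follow-up |
|---|---|---|---|
| 183 | 0 | 1 | 0.5% |
| 190 | 0 | 8 | 4.2% |
| 197 | 0 | 15 | 7.6% |
| 211 | 0 | 29 | 13.7% |

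**With the 183-day limit.** The same subject keeps 0 PDPEs and the observed follow-up: 183/365.25 = 0.501 years at Day 183, 0.539 at Day 197 and 0.578 at Day 211.

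**Scale per subject, under assumptions.** The documents give neither the number of such subjects nor an expected PDPE rate. For illustration, assume 211 subjects per arm (about half of the 423 randomized) followed for 0.5 years each, or 105.5 person-years, and a true rate of 0.3 to 1.0 per person-year. That is about 32 to 106 PDPEs per arm. One affected subject, withdrawn at Day 197 with 1 assigned PDPE, raises that arm's crude rate by 3.2% at the low end of the assumed rate and by 1.0% at the high end. These are changes in one arm's crude rate, not predictions for the modelled rate ratio.

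**The case against.** The best defense is that the intended meaning is plain. The rule sits under headings about missing data, setting follow-up to 26 weeks makes most sense when less was observed, and Sensitivity Analysis 3 shows that the authors' horizon was Day 183. That is a fair account of the intent. It does not change the four visible statements of the rule, none of which carries the limit, and a programmer following them would impute. Redacted SAP appendices could hold a programming limit, but nothing visible says so.

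The second defense is that the group may be empty, and this largely stands. To gain an event, a subject must pass Day 183, have no PDPE, have a prior-year count of at least 1, not complete Visit 4, and be recorded as withdrawn. Visit 4 completers are excluded by Protocol 9.1. Protocol 9.3 asks withdrawing subjects to attend their next scheduled visit, which after Week 26 is Visit 4.

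A reader might infer three stronger things that the documents do not support:

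- *That late withdrawals are expected, because SAP 7.1.2 tabulates withdrawal in weeks 26 to 31 and beyond.* Those intervals also report numbers at risk. Completers are censored at last participation, and the Visit 4 window plus the final call keep them at risk to about Week 31. The intervals are needed even if nobody withdraws late.
- *That adding the limit would let Sensitivity Analysis 3 isolate the effect of single imputation.* It would not. That analysis also imputes for withdrawals who already had a PDPE, adds imputed to observed events, and uses a different imputation model. The main rule covers only PDPE-free withdrawals. The two would still differ in whom they impute.
- *That the rule works against a particular arm.* SAP 8.1.1 cites higher drop-out on mannitol in the two previous trials, but that is overall drop-out, not withdrawal after Week 26.

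**Conclusion.** The point holds as a boundary error in a stated rule. Taken literally, the rule gives a wrong value for a PDPE-free subject withdrawn on or after Day 183 without Visit 4: 1 or 2 PDPEs where 0 were observed (for h of 1 to 8), and 1 to 29 days of observed follow-up removed for withdrawals up to Day 211. With h = 0, only the follow-up is affected. The problem lies in who is imputed, so it would remain without the rounding.

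Its practical weight is low. The group is probably very small and possibly empty, and its effect on the rate ratio cannot be derived from the documents. The endpoint is formally tested only after the primary and four earlier secondary endpoints succeed. Sensitivity Analysis 1, with no imputation, keeps observed counts and follow-up and would reveal an effect, although mixed with the effect of dropping all other imputations; it stands outside the testing hierarchy. This is a minor correction, worth making because it is simple and uses a limit that the SAP already contains.

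**What to change.** In SAP 8.2.5 (Missing Data), SAP 6.3 and the Table 6 rows that repeat the rule, restrict the imputation to withdrawals with follow-up duration shorter than 183 days, the limit already used in Sensitivity Analysis 3. State that later withdrawals are analyzed with their observed PDPE count and observed follow-up. Because Protocol 10.2.9 contains the unlimited rule, record the change in SAP Section 11.

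The cost is one phrase in each place, one Section 11 entry and one condition in the program. No new data are needed.

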## Statistical Analysis Plan

### 8.2.5.1. Sensitivity Analyses of Rate of Protocol Defined Pulmonary Exacerbations

#### Sensitivity Analysis 1: No Imputation

To elicit insights into the effect of the imputation method described above, the analysis will be repeated with no imputation of missing data.

#### Sensitivity Analysis 2: Zero Inflated Negative Binomial Model

To account for the possibility of an excess reporting of zero rates, the main analysis outlined above will be repeated using a zero inflated negative binomial model. This models the data as a mixture of two separate distributions; as a negative binomial distribution that can generate both zero and nonzero counts, and as a constant distribution that generates only zero counts. First an investigation of the data will be carried out to assess whether the probability of observing zero counts is conditional on any of the covariates in the model, by plotting the marginal and conditional distributions of the response variable.

[Redacted]

[Redacted]

[Redacted]

#### Sensitivity Analysis 3: Multiple Imputation

To assess the possible impact of employing a single imputation method (i.e. risk of variability underestimation), an analysis based on MI will be performed.

For all subjects who withdrew from the trial with a follow-up duration shorter than 183 days (i.e. 26 weeks+1 day), the number of PDPEs from withdrawal up to day 183 will

## Statistical Analysis Plan

be imputed.

The imputation will be performed using a model for the number of IV antibiotic treated PEs in the year prior to screening including rhDNase use and pooled country. Therefore, the imputation will be based on the distribution of historical PE count.

One thousand imputations will be performed and the analysis of the total number of PDPEs (observed+imputed events) will be based on the same negative binomial model described in the 'Analysis Method' paragraph above. Estimates from the models will then be combined using Rubin's rule.

### 8.2.5.2. Supportive Analysis of Rate of Protocol Defined Pulmonary Exacerbations

#### 8.2.5.2.1. Supportive Analysis - Rate of Pulmonary Exacerbations

##### Supportive Analysis: Single imputation, Pulmonary Exacerbations

Same approach as for the analysis described in 'Analysis Method' (Section 8.2.5), considering PEs (i.e. all PEs recorded on the CRF with associated antibiotic use, whether or not they met the criteria for a PDPE).

### 8.3. NON-HIERACHICAL SECONDARY EFFICACY ENDPOINT(S) AND ANALYSES

#### 8.3.1. Incidence of Protocol-Defined Pulmonary Exacerbations

##### Descriptive Summaries:

Incidence of PDPEs (yes or no) will be summarized as described in Section 8.2.5.

##### Analysis Method:

Proportions will be compared between treatment groups using logistic regression. The model will include the categorical effects pooled country, rhDNase use, and the continuous covariate number of IV antibiotic treated PEs in year prior to screening. The treatment group effect odds ratio, 95% CI, and p-value will be presented.

No imputation of missing data will be performed.

Pharmaxis Ltd

DPM-CF-303

Final v1.0

## Statistical Analysis Plan

### 8.3.1.1. Supportive Analysis of Incidence of Protocol Defined Pulmonary Exacerbations

#### Supportive Analysis: Incidence of Pulmonary Exacerbations

The summary and analysis defined in Section 8.3.1 will be repeated for incidence of PEs (i.e. all PEs recorded on the CRF with associated antibiotic use, whether or not they met the criteria for a PDPE).

### 8.3.2. Ease of Expectoration Visual Analogue Scale

#### Descriptive Summaries:

The ease of expectoration VAS score and absolute change from baseline will be summarized by visit using summary statistics for continuous variables, based both on actual data and imputed missing data.

#### Analysis Method:

The mean absolute change from baseline VAS score over Weeks 6, 14 and 26 will be compared between the two treatment groups with a REML based MMRM approach. The analysis will be the same as described for the primary endpoint in Section 8.1.1. The model will include the fixed, categorical effects of treatment group, rhDNase use, pooled country, visit, and treatment group-by-visit interaction, as well as the continuous, fixed covariates of baseline VAS score and disease severity (percent predicted FEV1 at baseline). Missing data will be handled in the same way as for the primary analysis of the primary endpoint.

### 8.3.2.1. Sensitivity Analysis of Ease of Expectoration Visual Analogue Scale

#### Sensitivity Analysis: MMRM Without BOCF

To elicit insights into the effect of imputation via the planned BOCF+IUDR framework, the main analysis outlined in Section 8.3.2 'Analysis Method' will be repeated with no imputation of missing data.

[figure not shown]
### 8.3.3. CFQ-R Respiratory Domain

#### Descriptive Summaries:

The CFQ-R respiratory domain scaled score and absolute change from baseline will be summarized by visit using summary statistics for continuous variables, based both on actual data and imputed missing data.

#### Analysis Method:

The mean absolute change from baseline in the CFQ-R respiratory domain score over Weeks 6, 14 and 26 will be compared between the two treatment groups with a REML

## Statistical Analysis Plan

based MMRM approach. The analysis will be the same as described for the primary endpoint in Section 8.1.1. The model will include the fixed, categorical effects of treatment group, rhDNase use, pooled country, visit, and treatment group-by-visit interaction, as well as the continuous, fixed covariates of baseline CFQ-R respiratory domain score and disease severity (percent predicted FEV1 at baseline). Missing data will be handled in the same way as for the primary analysis of the primary endpoint.

### 8.3.3.1. Sensitivity Analysis of CFQ-R Respiratory Domain

#### Sensitivity Analysis: MMRM Without BOCF

To elicit insights into the effect of imputation via the planned BOCF+IUDR framework, the main analysis outlined above will be repeated with no imputation of missing data.

### 8.3.3.2. Supportive Analysis of CFQ-R Domain

#### Supportive Analysis: MMRM with BOCF+IUDR Imputation, Question 42 Excluded

The above summary and analysis will be repeated for the CFQ-R respiratory domain score omitting Question 42 (CRF Question 3: “Have you had to cough up mucus?”), where the baseline covariate will be baseline CFQ-R respiratory domain score omitting Question 42.

## 8.4. SUMMARY OF ANALYSES

Table 6: Summary of Analyses

Analysis Designation	Endpoint	Model	Imputation Process Used	Off-trial Medication Data Included	Analysis Set
Primary					
Primary	FEV 1 Absolute Change from Baseline	MMRM	IUDR (trial withdrawal reason)/ BOCF	Yes	ITT
Primary - Sensitivity 1	FEV 1 Absolute Change from Baseline	ANCOVA	Pattern Mixture: MI Based on Reasons for Trial Withdrawal	Yes	ITT

## Statistical Analysis Plan

Analysis Designation	Endpoint	Model	Imputation Process Used	Off-trial Medication Data Included	Analysis Set
Primary - Sensitivity 2	FEV 1 Absolute Change from Baseline	ANCOVA	Tipping point	Yes	ITT
Primary - Sensitivity 3	FEV 1 Absolute Change from Baseline	MMRM	None	Yes	ITT
Primary - Sensitivity 4	FEV 1 Responders	Logistic Regression	Missing = non-response	Yes	ITT
Primary - Supportive 1	FEV 1 Absolute Change from Baseline	MMRM	IUDR (trial withdrawal reason)/BOCF	Yes	PP
Primary - Supportive 2	FEV 1 Absolute Change from Baseline - At Week 6/Week 14/Week 26	MMRM	IUDR (trial withdrawal reason)/BOCF	Yes	ITT
Primary - Supportive 3	Percent Predicted FEV 1 Absolute Change from Baseline	MMRM	IUDR (trial withdrawal reason)/BOCF	Yes	ITT
Primary - Supportive 4	FEV 1 Relative Change from Baseline	MMRM	IUDR (trial withdrawal reason)/BOCF	Yes	ITT
Primary - Supportive 5	Percent Predicted FEV 1 Relative Change from Baseline	MMRM	IUDR (trial withdrawal reason)/BOCF	Yes	ITT
Primary - Supportive 6	FEV 1 Absolute Change from Baseline	MMRM	IUDR (trial medication discontinuation reason)/BOCF	No	ITT

## Statistical Analysis Plan

Analysis Designation	Endpoint	Model	Imputation Process Used	Off-trial Medication Data Included	Analysis Set
Primary - Supportive 7	FEV 1 Absolute Change from Baseline	ANCOVA	Pattern Mixture: MI Based on Reasons for Trial Medication Discontinuation	No	ITT
Primary - Supportive 8	FEV 1 Absolute Change from Baseline	MMRM	None	No	ITT
Primary - by Subgroups	FEV 1 Absolute Change from Baseline	MMRM by Subgroups (see Section 6.6)	IUDR (trial withdrawal reason)/BOCF	Yes	ITT
Primary - by Subgroups	FEV 1 Relative Change from Baseline	MMRM by Subgroups (see Section 6.6)	IUDR (trial withdrawal reason)/BOCF	Yes	ITT
Secondary Hierarchical					
Secondary 1 Hierarchical	FVC Absolute Change from Baseline	MMRM	IUDR (trial withdrawal reason)/BOCF	Yes	ITT
Secondary 1 - Sensitivity 1	FVC Absolute Change from Baseline	ANCOVA	Pattern Mixture: MI Based on Reasons for Trial Withdrawal	Yes	ITT
Secondary 1 - Sensitivity 2	FVC Absolute Change from Baseline	MMRM	None	Yes	ITT
Secondary 1 - Supportive	FVC Absolute Change from Baseline - At Week 6/Week 14/Week 26	MMRM	IUDR (trial withdrawal reason)/BOCF	Yes	ITT

